## Methods

### Design

This study was a single-blinded randomized, placebo-controlled trial. The study was registered on ClinicalTrials.gov (NCT03112473) and conducted in our neurorehabilitation laboratory. Informed consents were obtained before the study began. The study protocol was approved by the ethics committee of the Hong Kong Polytechnic University and conducted in accordance to the Declaration of Helsinki.

As there was no previous study investigating the effect of Bi-TENS+TOT in improving the upper limb motor control in people with stroke, the effect size (Cohen's  $d=0.314$ ) used for the calculation of sample size in this study was obtained from our pilot trial. The sample size was calculated by using G\*power version 3.1.0 (Franz Faul, Universitat Kiet Germany) with  $\alpha$  of 0.05, power of 0.80, correlation among measure of 0.5 and non-sphericity correlation of 1. Ninety-six subjects were necessary to detect a significant between-group difference in the improvement of the upper limb motor control measured by FMA-UE. In accordance to our previous clinical trial, dropout rate of was assumed to be 20%, so a buffer of 24 subjects would be included. A sample size of 120 (30 per group) was used to detect the significant between-group difference finally.

The randomization was conducted by a research assistant who did not involve in the intervention and assessment after the baseline measurement. The eligible subjects were stratified into one of the four groups randomly: Bi-TENS+TOT group, Uni-TENS+TOT group, Placebo-TENS+TOT group and Control group. The stratification was conducted by the online software "Minimize". The factors of age (50-60, 60-70,>70), sex (male, female), type of stroke (ischemia, hemorrhage) and side of lesion (left, right) were balanced in the four groups. To achieve concealment, the allocation information was kept by the research assistant. Following the provision of informed consent, subjects were informed of their allocation to one of four groups, but specific group allocation remained concealed to maintain the blinding of treatment.

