## **Intervention**

### TENS protocol

With reference to previous studies, the dosage of 20 sessions of 60-minute TENS could provide sufficient stimulus to elicit recovery of motor function in people with chronic stroke. In the Bi-TENS group, the subjects received TENS on both paretic and non-paretic sides of the upper limbs. In the Uni-TENS group, TENS was only applied on the paretic side of the upper limb while a placebo stimulation (P-STIM) was applied on the non-paretic side. In the Placebo-TENS+TOT group, the P-STIM was applied on both sides of the upper limbs. In the Control group, the subjects did not receive any active treatment. The disposable surface electrodes were applied to stimulate the median nerve (from the carpal tunnel to flexor digitorum superficialis) and superficial radial nerve (from the extensor pollicis longus to extensor digitorum communis).

The stimulator was 120z Dual-Channel TENS Unit (ITO PHYSITHERAPY&REHABILITATION CO., LTD, Tokyo, Japan). The parameter (100 Hz, 0.2 ms square pulses, intensity barely below the motor threshold) of TENS followed our previous study (10). The P-STIM was provided by identical-looking TENS devices that electrical circuit has been disconnected.

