#### **Outcome Measure**

To eliminate the bias, an experienced rehabilitation therapist who was blinded to the group allocation assessed all outcome measures in a random sequence for 5 times, including baseline, mid-intervention (4th week of study), post-intervention (8th week of study), 1-month follow-up and 3-month follow-up.

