### Statistical Analysis

All the quantitative analyses were performed by the SPSS (Version 23.0, IBM, Armonk, NY). Descriptive analysis was used to summarize subjects' demographic information. One-way analysis of variance, Chi-Squared test ( $\chi^2$  test) and Kruskal-Wallis test were used to compare the baseline characteristics of the four groups as appropriate. Intention-to-treat analysis (last observation carry forward) was used. The linear mixed models (LMM) were used to compare the changes over time in variables of interest between those in the Bi-TENS+TOT group and those in the Uni-TENS+TOT group, Placebo-TENS+TOT group and Control group. The maximum likelihood estimation was used to selected the best fit model. The first-order autoregressive structure with heterogeneous variances (AR (1): heterogeneous) was used to estimate the

parameters of statistical model. The intervention effect from pre-intervention to post-intervention was analyzed by LMM. The carryover effect from post-intervention to 3-month follow-up assessment was analyzed using the same LMM method. The significant level was set at 0.05. The post-hoc analysis would be conducted by Bonferroni correction when there was an overall significant difference.

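### The 80% power stated at 96 subjects is not power for a Cohen's d of 0.314 between Bi-TENS+TOT and another arm; at the plan's own correlation that contrast has about 19% power

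*Combined protocol and SAP*

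**What the plan says.** The sample size paragraph under Design gives a Cohen's d of 0.314, which was "used for the calculation of sample size in this study was obtained from our pilot trial". The other inputs are alpha 0.05 and "power of 0.80, correlation among measure of 0.5 and non-sphericity correlation of 1", entered in G\*Power. It concludes that "Ninety-six subjects were necessary to detect a significant between-group difference in the improvement of the upper limb motor control measured by FMA-UE". Twenty-four subjects are added for 20% dropout: "A sample size of 120 (30 per group) was used to detect the significant between-group difference finally". The paragraph does not name the G\*Power test, the number of measurements, the f entered, or the contrast that d describes.

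Under Outcome Measure there are five assessments: "baseline, mid-intervention (4th week of study), post-intervention (8th week of study), 1-month follow-up and 3-month follow-up". Under Statistical Analysis, "The intervention effect from pre-intervention to post-intervention was analyzed by LMM", so the main period covers the first three. The same section says "The linear mixed models (LMM) were used to compare the changes over time in variables of interest between those in the Bi-TENS+TOT group" and each of the other three arms, with Bonferroni post-hoc tests after a significant overall result.

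**The concern.** Cohen's d is a standardised difference between two means. When it is paired with a between-group difference in improvement, and the analysis section then names three two-arm comparisons, a reader will take the trial to have 80% power for a 0.314 SD advantage of Bi-TENS+TOT. With 24 subjects per arm that is not plausible.

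Bi-TENS against Uni-TENS matters most here. Both arms receive active stimulation on the paretic side and differ only in whether the non-paretic side gets active or placebo stimulation, so this contrast isolates the bilateral component. If its power is much lower than the stated figure, a non-significant result says little, yet it could be read as a negative finding from a trial with 80% power.

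**Working it through.** **Inputs.** From Design: d = 0.314, alpha 0.05, power 0.80, correlation ρ = 0.5, non-sphericity 1, k = 4 arms, N = 96 (24 per arm) and 120 (30 per arm). From Outcome Measure and Statistical Analysis: m = 3 visits from pre- to post-intervention. Assumed: the interaction test, f = d/2, two-sided contrasts and complete data.

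**1. Reproducing 96 and 120.** For a within-between interaction, λ = f²Nm/(1−ρ), df1 = (k−1)(m−1), df2 = (N−k)(m−1). With f = 0.314/2 = 0.157:

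- N = 96: λ = 0.157² × 96 × 3/0.5 = 14.20, df 6 and 184, power 0.803.
- N = 92: power 0.783. So 96 is the smallest balanced total.
- With 2, 4 or 5 visits the total would be 116, 84 or 76.
- Dropout: 96/0.8 = 120.

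No other four-arm option tried gave 96. The arithmetic is sound for this test; the question is what effect it describes.

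**2. What f = 0.157 means with four arms.** The identity f = d/2 holds for two equal groups. For the interaction, at ρ = 0.5 (where the SD of change, √(2(1−ρ)) = 1, equals the outcome SD), f = R × g × h. Here R is the largest between-arm difference in change, g is the SD of the arm pattern per unit of R, and h is the SD of the time course over the three visits: √(1/6) = 0.408 if linear, √(2/9) = 0.471 if the whole effect appears either by mid-intervention or only after it.

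| Arm pattern | g | R for f = 0.157 (step; linear) | Omnibus power at N = 96 if R = 0.314 (linear; step) |
|---|---|---|---|
| Two arms against two | 0.500 | 0.67; 0.77 SD | 16%; 21% |
| One arm differs | 0.433 | 0.77; 0.89 SD | 13%; 16% |
| Even gradient | 0.373 | 0.89; 1.03 SD | 11%; 13% |
| Two extremes, two midway | 0.354 | 0.94; 1.09 SD | 10%; 12% |

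So f = 0.157 implies a largest arm difference of about 0.67 to 1.09 SD, at least twice 0.314. Conversely, if 0.314 SD is the largest difference between any two arms, f is 0.314 × 0.354 × 0.408 = 0.045 up to 0.314 × 0.500 × 0.471 = 0.074. Omnibus power is then 10–21% at N = 96 and 12–26% at N = 120.

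**3. A single Bi-TENS contrast of 0.314 SD.** Two-sample noncentral t on change, with noncentrality d√(n/2) and df = 2n − 2. For n = 24 this is 0.314 × √12 = 1.088.

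| | 0.05 | 0.05/3 |
|---|---|---|
| Power, 24 per arm | 18.7% | 9.0% |
| Power, 30 per arm | 22.3% | 11.4% |
| Difference detectable at 80%, 24 per arm | 0.83 SD | 0.96 SD |
| Difference detectable at 80%, 30 per arm | 0.74 SD | 0.86 SD |

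Pooling the error df over four arms (92 at 24 per arm) moves 18.7% only to 19.0%. This step does not depend on the set-up inferred in step 1.

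**4. Sensitivity to the correlation.** If d is in outcome-SD units, the effect on change is d/√(2(1−ρ)). With 24 per arm at 0.05, ρ = 0.9 gives 0.314/√0.2 = 0.702 and 66% power; ρ = 0.93 gives 0.314/√0.14 = 0.839 and 81%. With 30 per arm the figures are 76% and 89%. The values of ρ above 0.5 are assumptions, not plan figures.

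**The case against.** The strongest reply is that the paragraph never promises 80% power for each Bi-TENS contrast. Correlation and non-sphericity are repeated-measures inputs, there are four groups, and the post-hoc tests follow an overall test, so the 80% may simply be omnibus power. If 0.314 was itself obtained as 2f from the pilot's group-by-time effect, the 80% is exactly right for that test. This stands, and it is why the point concerns what the figure refers to and not the sum. It does not remove the point: the text labels the effect Cohen's d, and 80% omnibus power at f = 0.157 is still not power for a 0.314 SD contrast.

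A reader might infer that Bi-TENS against Uni-TENS has about 9% power at 0.05/3 on any reading. The documents do not support that. One possible pattern has adjacent arms stepping evenly by 0.314 SD, which is conceivable because "In the Control group, the subjects did not receive any active treatment". Omnibus power is then 71–85% at N = 96, the extreme arms lie 3 × 0.314 = 0.94 SD apart, and Bi against Uni has 9%. But this is not the reading kindest to the plan. If 0.314 is 2f and Bi-TENS alone differs, its lead is 0.77–0.89 SD and power at 0.05/3 is 57–72% with 24 per arm (70–83% with 30).

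A reader might also infer that contrast power stays below 80% at any correlation. It does not if d is in outcome SDs: it passes 80% from about 0.93. The FMA-UE test-retest figure of 0.965 under Primary Outcome shows that high values are not absurd, although that figure is probably an upper limit over eight weeks of treatment, and the plan itself uses 0.5.

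**Conclusion.** The concern holds in conditional form. The 96 and the 120 are not in error. As worded, though, the 80% is attached to an effect for which a two-arm comparison in this design, at the plan's correlation of 0.5, has about 19% power at 0.05 and 9% at 0.05/3 with 24 per arm (22% and 11% with 30).

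The contrast figures rest on ρ = 0.5 or on d being on the change scale, and on a t-test approximation to the mixed model with complete data. The omnibus figures, including the 0.67–1.09 SD translation, rest also on the inferred set-up of four arms, three visits and f = d/2, and on the arm patterns and time courses listed. The documents do not show which contrast 0.314 describes, so they do not establish that the overall test is underpowered: its power at N = 96 is 10–21% if 0.314 SD is the largest arm difference, and 80% if 0.314 is 2f.

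**What to change.** Restate the sample size paragraph so that the 80% refers to the omnibus group-by-time test. Name the G\*Power option, the number of visits, the f entered and the contrast behind 0.314. If the inferred set-up is confirmed, the text could read: 96 evaluable subjects (24 per group) give 80% power for the omnibus group-by-time interaction over three visits at f = 0.157, corresponding to a largest between-arm difference in change of about 0.67 to 1.09 SD depending on the pattern; a single Bi-TENS contrast has 80% power for about 0.83 SD at 0.05 or 0.96 SD at 0.05/3. If another set-up was run, give the same statement for that test.

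Report confidence intervals for the three Bi-TENS contrasts, so that a non-significant Bi-TENS against Uni-TENS result is not taken as evidence of no difference.

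The cost is wording only. The overall test and the Bonferroni step can stay, and no extra subjects are needed, which matters because the Subjects section reports all 120 as recruited. The downside is a less favourable stated sensitivity.

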## **Subjects**

One hundred and twenty subjects (mean age=61.70±5.91 years) were recruited from the local self-help groups. The inclusion criteria of the subjects included: (1) were between 50 and 80 years of age; (2) had been diagnosed with stroke within 1 to 10 years; (3) had volitional control of the non-paretic arm and at least minimal antigravity movement in the paretic shoulder; (4) had at least 5 degrees in wrist extension in the antigravity position; (5) had an Abbreviated Mental Test score  $\geq 7$ . The participants were excluded if they: (1) had any additional medical, cardiovascular or orthopedic condition; (2) had contraindications to TENS, such as implant cardiac pacemaker, skin allergy; (3) had receptive dysphasia; (4) had a significant upper limb peripheral neuropathy; (5) were involved in drug studies or other clinical trials; (6) had severe shoulder, elbow, wrist or finger contractures.

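### Baseline FMA-UE is neither a minimisation factor nor a stated model covariate, so each Bi-TENS+TOT comparison carries about a 22% chance of a baseline gap of 0.314 SD or more

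*Combined protocol and SAP*

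**What the plan says.** Design describes four arms of 30, allocated with minimisation software. The balancing factors are given as "The factors of age (50-60, 60-70,>70), sex (male, female), type of stroke (ischemia, hemorrhage) and side of lesion (left, right) were balanced in the four" arms. None of them measures arm impairment.

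Subjects limits impairment from below only. Besides minimal antigravity shoulder movement, each subject "had at least 5 degrees in wrist extension in the antigravity position". Severe contractures are excluded, but there is no upper limit on arm function.

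Primary Outcome names FMA-UE, with a total of 66. Outcome Measure has a blinded therapist score it at baseline and at four later visits. Design says allocation was done by "a research assistant who did not involve in the intervention and assessment after the baseline measurement", which can be read as placing allocation after the baseline assessment, although the sentence is loosely worded.

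Statistical Analysis tests baseline characteristics across the four groups. It then uses a linear mixed model (LMM) to compare changes over time between Bi-TENS+TOT and each of the other three groups. It mentions no baseline covariate.

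**The concern.** Minimisation is used to protect a small trial against chance imbalance in factors that predict the outcome. The baseline value of the primary outcome is an obvious candidate, and here it is handled neither at allocation nor in the model as written. A subject just above the movement threshold and one near the top of the scale count as the same for allocation if they match on age band, sex, stroke type and lesion side.

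If one arm starts lower by chance, regression to the mean alone makes it gain more on average. A ceiling near 66 could add to this. A comparison of unadjusted change then partly reflects the starting gap. Testing for baseline differences may reveal the gap but does not remove it from the estimate.

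**Working it through.** **Inputs.** From Design: 30 per arm; pilot d = 0.314 (the effect size "used for the calculation of sample size in this study was obtained from our pilot trial"); "power of 0.80, correlation among measure of 0.5 and non-sphericity correlation of 1". From Statistical Analysis: "The significant level was set at 0.05", and three comparisons with Bi-TENS+TOT. From Primary Outcome: FMA-UE test-retest r = 0.965.

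**1. The plan's own sample size.** Take a repeated-measures group-by-time interaction with f = 0.314/2 = 0.157, k = 4 groups and m = 3 measurements (baseline, mid, post):
- Noncentrality = f² × N × m / (1 − ρ) = 0.02465 × 96 × 3 / 0.5 = 14.2.
- df = (3 × 2, 92 × 2) = (6, 184).
- Power = 0.803 at N = 96, and 96/0.80 = 120.

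Both stated figures reproduce. So 0.314 entered the plan as an interaction effect. Used below as a size of baseline gap, it is only a rough benchmark.

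**2. Chance of a baseline gap.** For a variable not balanced by design, the standardised difference between two arms of 30 has SE = √(2/30) = 0.258.
- One comparison: 2 × [1 − Φ(0.314/0.258)] = 2 × [1 − Φ(1.216)] = 22.4%.
- At least one of the three Bi-TENS+TOT comparisons, by simulation: 47.5%.

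If the four factors explain a share R² of FMA-UE variance (assumed; the documents give none), the SE is multiplied by √(1 − R²):

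| R² | One comparison | At least one of three |
|---|---|---|
| 0 | 22.4% | 47.5% |
| 0.1 | 20.0% | 43.3% |
| 0.3 | 14.6% | 33.2% |

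**3. Effect on the change comparison.** Assume equal SDs over time and a model that leaves each group's baseline mean free. The expected shift in the difference in change is then (1 − ρ) × gap, in favour of the arm that started lower:

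| ρ | Shift for a 0.314 SD gap |
|---|---|
| 0.5 | 0.157 SD |
| 0.7 | 0.094 SD |
| 0.9 | 0.031 SD |
| 0.965 | 0.011 SD |

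The SE of the difference in change also shrinks as ρ rises. It is 0.258 × √[2(1 − ρ)], which is 0.258 at ρ = 0.5 and 0.115 at ρ = 0.9. The shift is therefore 0.61 SE at 0.5 and 0.27 SE at 0.9.

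**4. Conditional error rate.** Given the baseline gap, the SD of the estimated difference in change is 0.258 × √(1 − ρ²). With no true effect and a two-sided 0.05 test (before any Bonferroni correction), the chance of significance in the favoured direction is:
- ρ = 0.5: 1 − Φ[(0.506 − 0.157)/0.224] = 5.9%, against 1.2% with no gap.
- ρ = 0.9: 1 − Φ[(0.226 − 0.031)/0.113] = 4.2%, against 2.2% with no gap.

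Averaged over all possible gaps, the rate is the nominal 2.5% in each direction.

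**5. Precision.** The variance of an unadjusted change comparison is proportional to 2(1 − ρ); after baseline adjustment it is proportional to 1 − ρ². At ρ = 0.5 this is 1.00 against 0.75, a 25% reduction. At ρ = 0.9 it is 0.20 against 0.19, a 5% reduction.

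**6. What balancing would do.** Near-perfect balance on a median split of normally distributed scores (explaining 64% of the variance) lowers the chances in step 2 to 4.4% and 11%. A simulation of minimisation with FMA-UE tertile as a fifth factor (1,500 runs, assumed factor mix, 80% best-arm probability) gave 3.5% and 8.4%. The assumptions behind both are not in the documents.

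**The case against.** The strongest case against is that this is a modest design preference. Four factors were chosen, chance imbalance under random allocation is already covered by the test's error rate, and the LMM analyses change rather than raw post-treatment scores. All of that stands, and it limits the point to conditional bias and precision.

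The correlation also matters. The 0.5 is a sample-size input. The test-retest value of 0.965 is not a baseline-to-week-8 correlation, but in subjects 1 to 10 years after stroke it makes a value well above 0.5 plausible. The shift could then be a small fraction of 0.157 SD.

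Three stronger readings are tempting, and the documents do not support them.
- A reader might infer that a gap as large as the trial's effect size is likely. It is about one in five for a given comparison and just under even for any of three, and less if the existing factors predict FMA-UE.
- A reader might equate a 0.314 SD baseline gap with a bias of that size. The 0.314 was sized as differential change over time, and at most about half of such a gap carries through over the correlations shown.
- A reader might conclude that the shift could never be told apart from a treatment effect. Baseline FMA-UE is scored at baseline by a blinded assessor, so adjustment would separate most of it.

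Finally, Design and Subjects are in the past tense and report 120 subjects recruited. A fifth allocation factor may therefore no longer be possible.

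**Conclusion.** The concern holds as a moderate, inexpensive weakness; it does not threaten validity. The primary outcome's baseline value is left out of both the allocation and the stated model, eligibility sets no upper limit on arm function, and the arms are small. The step 2 chances rest on 30 per arm and on how much of the FMA-UE variance the four factors explain. The size of the consequence rests on the baseline-to-post correlation, which the documents give only as a planning value, and on equal SDs over time. Even at 0.9, a gap of this size nearly doubles the conditional false-positive rate in the favoured direction (2.2% to 4.2%), so the point does not vanish at high correlation. The plan's baseline significance tests offer no protection. Baseline adjustment would, and it is not specified.

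**What to change.** If allocation is still open, add a baseline FMA-UE category as a fifth minimisation factor, for example three bands of the 0-66 score fixed in advance. State plainly that allocation follows the scoring of the baseline FMA-UE. Include that factor, or preferably the continuous baseline score, in the LMM.

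If allocation is complete, as the text suggests, adjust the LMM for continuous baseline FMA-UE. Say in the analysis section that this adjustment, and not the baseline significance tests, deals with imbalance.

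The cost is one more field in software already in use, slightly looser balance on the other four factors, and one more model term. No extra visits, staff or subjects are needed, because FMA-UE is already scored at baseline.

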## **Subjects**

One hundred and twenty subjects (mean age=61.70±5.91 years) were recruited from the local self-help groups. The inclusion criteria of the subjects included: (1) were between 50 and 80 years of age; (2) had been diagnosed with stroke within 1 to 10 years; (3) had volitional control of the non-paretic arm and at least minimal antigravity movement in the paretic shoulder; (4) had at least 5 degrees in wrist extension in the antigravity position; (5) had an Abbreviated Mental Test score  $\geq 7$ . The participants were excluded if they: (1) had any additional medical, cardiovascular or orthopedic condition; (2) had contraindications to TENS, such as implant cardiac pacemaker, skin allergy; (3) had receptive dysphasia; (4) had a significant upper limb peripheral neuropathy; (5) were involved in drug studies or other clinical trials; (6) had severe shoulder, elbow, wrist or finger contractures.

